Usage errors relating to medical devices that led to death or serious deterioration of the state of health or to a serious danger to public health must be reported by the manufacturer to the Ministry of Health when the manufacturer notices a significant change in the trend (typically an increase in frequency) or a significant change in the way a problem presents itself that could potentially lead to death or serious deterioration in health or represent a danger to public health, or the manufacturer takes corrective action to prevent a death, a serious deterioration in health or a serious danger to public health. Abnormal use does not necessarily have to be reported by the manufacturer to the Ministry of Health according to the reporting procedures. Abnormal use should be managed by the health facility. If a manufacturer becomes aware of abnormal use cases, he can bring them to the attention of other appropriate organizations and health facility personnel.

Safety follow-up of subjects withdrawn from the Study or who have completed the same

Each morbid condition derived from each patient's accident will be monitored throughout the whole study period. The subjects that withdrew from the experimentation after the treatment with the device under study for any reason, will undergo a continued monitoring of the effects of the accident until the results from the tests related to the adverse event, and required by the SOC, will recover to baseline or until the investigator will determine that those events are not clinically relevant anymore.

All the subject who still present ongoing effects of an accident upon completion of the study will be monitored until the test results are not back to baseline, or is no longer expected from them to

change, or until the investigator does not determine that those results are no longer clinically relevant.

Amendments to the clinical evaluation plan

If, during the study, a modification to the protocol is deemed necessary, the investigator communicates this need to the sponsor, who convenes the investigator, the study director and any other experts in the field, and discusses the proposed variations and, where appropriate, submits a request for amendment to the Ethics Committees to approve the changes deemed necessary. If a substantive amendment request is necessary, the clinical trial will be suspended until approval has been received by the relevant ethics committees.

Early termination and suspension of clinical evaluation

In the event of suspension or early termination of the study by the promoter, taken as a safety measure due to events related to the conduct of the study that may affect the health of the patients recruited, the promoter is required to notify the Ministry of Health and the Ethics Committees involved within 90 days from the recruitment of the last patient or the early closure. In case of suspension or early termination of the study not for safety reasons, the sponsor shall justify and explain their decision. The suspended clinical trial cannot be reactivated unless a substantive amendment and the positive opinion of the Ministry of Health and the Ethics Committees have been submitted.

Statistics

Calculation of the sample number

Lack of reliable data in the scientific literature on average recovery times of decubitus ulcers (PUs), the absence of clinical experience combining blue light treatments with the therapy of this type of lesion, and the lack of reliability about any inference based on clinical studies that associate this type of treatment with other types of skin lesions, due to the different aetiologies and types of patients, do not make possible to perform a reliable calculation of the sample number. The predefined sample size was therefore set on the basis of considerations concerning the recruitment capacity of the centre involved in the project. Based on an estimate of the historical clinical activity data at the Cardiorespiratory Rehabilitation Units, at the Neuro-Motor Rehabilitation Unit and at the Acquired Severe Brain Injury Unit (UGCA), where patients will be enrolled, the percentage of patients with decubitus ulcers at the entrance is about 20%, an information that implies that compared to an average of about 426 patients/ year, in 10 months of enrollment it is possible to reach a number of 40 patients compared to a percentage of drop-out/ waste equal to about 25%. A total of 40 patients will be recruited, 20 patients with second stage PUs and 20 patients with third stage PUs. Thus, this study is intended as a "proof of concept", the results of which may be used as preliminary information to define the sample size in later studies.

Management of missing data

Since it is a "proof of concept" study based on a limited number of patients, we will include in the study also patients who do not conclude the study according to the principle "intention to treat" and the resulting missing data will be processed through the imputation technique of the missing data *last observation carried forward - LOCF*. If the patient does not leave the study but skips one or more visits, the averages of the two adjacent visits or the last available data (LOCF) will be taken into account.

Statistical analysis

Demographic and clinical data will be presented in tables and graphs in the form of frequencies and percentages for categorical variables, mean, standard deviation, median and interquartile range for continuous variables, differentiating by reference population and treatment group. At a first analysis a qualitative comparison will be carried out between the treatment groups (improvement or not improvement), both general and differentiated for lesion of 2° and 3° stage, through the χ^2 test or Fisher's exact test for counts of less than 5. The results will be presented in contingency tables and bar charts.

A quantitative comparative statistic between the treatment groups will then be performed by comparing the outcome variables (percentage reduction of the lesion area and reduction of the PUSH index) through the non parametric test of Mann-Whitney, one of the most powerful nonparametric tests used to verify whether two independent groups belong to the same population. The Mann-Whitney test is usually applied when the assumptions to perform the parametric test are not met, which means when the distribution of the variable under study is not normal and/or the sample sizes are reduced (n 30 cases in at least one sample).

In this case, the choice to perform a non parametric analysis lies in the low sample size and therefore it is preferred to have more conservative meaningfulness values. The results will be presented in tables, with median and interquartile interval in the two groups with the relative p. value, and graphically, through box plot.

To analyse the internal and between groups time-related differences, Friedman's non-parametric test for the outcome variables will be performed.

Generalized linear models (GLM) will be used to investigate whether differences between the two groups are influenced in a confounding way by demographic and clinical covariates, pre-treatment measurement, and to measure their impact that will allow us to understand which variables affect the outcome and will also allow us to analyse the differences between groups being equal for these covariates.

A descriptive statistic of adverse events, if present, will also be made through tables with frequencies and percentages, and bar charts.

All significance tests will have a statistically significant p. value <0.05. The analysis will be carried out with the open source software R Commander (v. 2.2-0).

croData publication policy

At the end of the clinical study and of the related analysis about the obtained results, these will be made available anonymously and aggregated in full respect of the protection of the right to privacy, in accordance with Regulation no. 2016/679 (GDPR, General Data Protection Regulation), for publication in national or international journals, or for presentation by investigators at scientific conferences and in medical journals. For the writing of any publications concerning the study in question, may be used professional medical writers who will write manuscripts on behalf of the company and for which the company undertakes to ensure analogous compliance with current legislation.

After the conclusion of the study, the sponsor will be responsible for drawing up the final report of the clinical trial in the manner and timing prescribed in the current legislation regarding clinical investigations; external consultants of the sponsor, experts in this field, may be involved in the preparation of the final report and for which the sponsor ensure the same compliance with current legislation.

References

1. Clark R (1985) Cutaneous tissue repair: basic biological considerations. *J Am Acad Dermatol* 13: 701-725.
3. Nwomeh BCM Yager DR, Cohen IK (1998) Physiology of the chronic wound. *Clinics in Plastic Surgery* 25 (3): 341
4. Hackam DJ, Ford HR (2002) Cellular, biochemical and clinical aspects of wound healing. *Surgical Infections* 3: S23-S35.
5. Calderhead (2007), The photobiological basis behind light-emitting diode (LED) phototherapy, *Laser therapy*.

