Pressure, that is often associated to a limitation in mobility of the patient, for a long time has been considered the most important extrinsic factor in the development of pressure ulcers.

However, recent research, and still ongoing, is revealing that shear forces, friction, and microclimate also play an important role in the etiology of pressure ulcers, and that, also, some significant and complex relationships between all these extrinsic factors exist.

In alert patients, the effects of prolonged pressure usually stimulate frequent light body movements to relieve the load and restore tissue perfusion. Unconscious, sedated, anesthetized or paralyzed patients cannot feel or respond to these stimuli and do not move spontaneously. As a result, skin and soft tissue can be exposed to prolonged and without relief pressure.

PUs are generally more common in anatomical locations that cover a bone prominence. In adults, the most common sites are the sacrum and the heel. Other frequently affected anatomical

locations are ischium, ankle, elbow and hip.

Pressure ulcers are often difficult to diagnose, in particular it is easy to confuse them with moisture-caused injuries. A correct diagnosis is essential to determine both prevention and treatment plans.

For a proper management of pressure lesions it is essential to take into account their characteristics (location, color, size, amount of exudate, type of tissue, smell, edges) and to consider the condition of the peri-lesional skin (erythema, edema, hardening, maceration). To describe the state of a pressure ulcer, EPUAP (European Pressure Ulcer Advisory Panel) and NPUAP (National Pressure Ulcer Advisory Panel) recommend to divide pressure injuries stages from 1 to 4:

- Stage 1 - Persistent erythema
Intact skin with redness not reversible to acupressure in a localized area, usually above a bone prominence. Stage 1 may indicate a patient at risk.
- Stage 2 - Partial thickness tissue loss
Loss of the dermis at partial thickness, which looks like a shallow and open ulcer, with red - pinkish lesion bed, without slough. It may also present as a vesicle, intact or open/broken, serous and/or haematic.
- Stage 3 - Total Thickness Tissue Loss
Loss of tissue at total thickness. Subcutaneous fat may be visible, but bones, tendons or muscles are not exposed. There may be slough, which does not hide the depth of tissue loss. It may include undermining wounds and tunneling.
- Stage 4 - Loss of subcutaneous tissue

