Furthermore, through the action on the T lymphocytes present in the wound bed, ROS are able to promote the phenotypic transition of macrophages from M1 (pro-inflammatory) to M2 (pro-healing) (15, 16). This combination of effects suggests a positive action on the inflammatory stasis that characterizes some types of "non-healing" wounds: an increase in inflammation such as to induce the body to a consistent response and the consequent stimulation for the following phases.

Through the production of HIF-1 α (Hypoxia-inducible factor 1-alpha) and the consequent release of proangiogenic factors and induction of eNOS (endothelial Nitric Oxide Synthase) ROS also play a role in promoting angiogenesis (17, 18) and therefore in the increase of the nutrient and oxygen supply in the wound bed, of great importance in the proliferation phase.

The device has been designed and set to deliver a power density of about 7 J/cm² in an acceptable treatment time for both doctor and patient (60 seconds).

[figure not shown]
The choice of the duration of the treatment was also made on the basis of what is stated in literature on thermal damage: the treatment induces a temperature between 45 and 50 °C in the treated area, ideal condition to stimulate the reversible and physiological phenomena that we want to induce.

Table 3.6. Thermal effects of laser radiation

Temperature	Biological effect
37°C	Normal
45°C	Hyperthermia
50°C	Reduction in enzyme activity, Cell immobility
60°C	Denaturation of proteins and collagen, Coagulation
80°C	Permeabilization of membranes
100°C	Vaporization, Thermal decomposition (ablation)
> 150°C	Carbonization
> 300°C	Melting

The physiological phenomena induced by temperature (11)

The same volume shows a curve that links the duration of the thermal stimulus with the reversibility of the process induced by this stimulus.

Critical temperatures for the occurrence of cell necrosis in relation to the duration of exposure (11).

This data on the physiological effects of temperature was the first constraint for the definition of treatment parameters.

In addition to studies related to the influence of temperature, the decision of treatment time is based on a finite element model (11) which correlates optical power, treatment time and final temperature induced by the treatment with the device in question. The initial model led to establish the conditions of optimal work, that were then tested in an animal model study.

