The present clinical study aims to verify the effectiveness and safety of the blue light photobiomodulation therapy with EmoLED medical device in supporting the reparative process of the area of the second and third stage decubitus lesion, comparing this method with the effectiveness of the therapy commonly used in the clinical field.

Ethical considerations

This Study will be conducted with reference to the standards of Good Clinical Practice and in accordance with the principles of the Declaration of Helsinki, with the UNI_ISO_14155_2020 norm, and with all relevant local laws and regulations, applicable to clinical trials that use patients as research object. This clinical investigation cannot begin in the involved center before having received the favorable written approval of the “Area Vasta Toscana Centro” Ethics Committee. The medical assistance provided to the subject is responsibility of adequately qualified doctors, as the center involved in this study is specialized in the treatment of the pathology object of the clinical trial.

During this trial, the patients' right to physical and mental integrity, the right to privacy and the protection of data concerning them will be respected in accordance with Directive 95/46 / EC.

This clinical investigation was designed to cause as little pain, discomfort, fear and other foreseeable risks for the subject as possible, and the degree of discomfort related to the trial itself or to the treatment with the medical device in question is almost nil, considering the Clinical Evaluation Report of the device and the safety data obtained from post-marketing surveillance.

The degree of discomfort / pain of the enrolled patients is however subject to continuous verification during the clinical trial, through a special questionnaire on the detection of discomfort connected to participating in the study in question. The risk / benefit ratio will be constantly checked throughout the trial, taking into account any adverse events / device-related accidents or non-serious side effects reported by the main investigators, and the preliminary assessment of the benefits about patients who have completed the study process.

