The safety and efficacy clinical validation to obtain the CE marking for the EmoLED device for the treatment of acute surgical wounds is ongoing. In particular, the acute observations, whose detailed results are provided in the attached final Report on the clinical trial, have once again demonstrated the device's safety and efficacy in shortening the healing time of spontaneously healing wounds. Isolated observations in patients with chronic lesions, of various aetiologies, have shown that the device is capable of unblocking the healing process, thus allowing the wound to progress beyond the inflammatory phase by inducing re-epithelialisation and wound closure. Observations made using a thermal camera have also shown that, due to the compromised condition of the tissues surrounding the ulcers, the baseline temperature of the limb is lower than normal and that both during and after treatment with the EmoLED device, the temperature never exceeds 40°C.

Information related to the clinical investigation

Study description

The commercial purpose of this study is to value the clinical efficacy of a battery-powered device that uses blue LEDs.

The study aims to compare the response of an existing standard treatment for second and third stage pressure sores, with a protocol that plans the administration of the EmoLED treatment three times a week for 4 consecutive weeks in addition to the conventional therapy.

Primary and secondary objectives

The primary objective of the study will be to assess the clinical efficacy of a treatment made through a battery-powered portable medical device that uses blue LEDs, in addition to the conventional therapy, applied on second and third degree pressure sores, compared to the conventional treatment alone, at the end of the fourth week of observation. As secondary objectives, the study proposes the clinical evaluation of lesions during the 4 weeks of treatment, and the evaluation of the treatment’s safety.

Endpoints

Primary endpoint of the study

The primary endpoint of the study is the assessment of the clinical state of second and third stage ulcers by reducing the index of the PUSH scale, in the two treatment groups at the end of the 4-week observation period.

Secondary endpoints

1. The assessment, during the weeks of observation, of the percentage of reduction of the lesion area compared to V0 in the second and third stage lesions in the two treatment groups;

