If the patient has two or more decubitus lesions at the same stage, the doctor will choose to treat the lesion of which, in his opinion, the data acquisition (photography and size measurement) is better. If a patient has two or more lesions of different stages, the doctor will decide to include in the study only one of them, based on the number of lesions inserted at that time in the two groups, choosing the group with a smaller number: In this way, attempts are made to ensure a numerical trend as simultaneous as possible in the two groups of lesions (e.g. if the number of 2°stage lesions enlisted is less than the number of 3°stage lesions enlisted, then the 2°stage lesion will be included in the study). In the case of a numerical parity of the two groups of lesions, the doctor will decide to treat the lesion with a position that allows a better data acquisition (photographic image, measurement, etc.).

Case Report Forms

Case Report Forms are unique to every patient. It will be used the form of injury assessment already present at the Investigator Centre; the data collection by the Principal Investigator includes: patient's name and surname, date of birth, room number, medical record number, date of surgery, any allergies and the characteristics of the lesion under investigation -position and degree of the lesion-. Another section dedicated to the characteristics of the lesion, includes: dimensions (length x width), the amount of exudate and the type of tissue. All these features will be evaluated, according to the criteria of the international scale PUSH, with a score, specified in the legend in the form, of which the total will be reported at each visit.

The Pressure Ulcer Scale for Healing (PUSH) is a tool designed by the National Pressure Ulcer

Advisory Panel (NPUAP) and used to observe the trend of pressure ulcers over time, classifying them regarding the area of extension, the exudate and the tissue type, noting the partial score for each characteristic of the ulcer and summing those scores to obtain the total. Comparing the relevant total scores over time will provide an indication of the improvement or worsening of the healing of the pressure ulcer.

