In addition, the data collected with the CRF, and other data from the medical records of patients enrolled, will be grouped and reported, in pseudonymized form, in a computerized database on three forms, generated with Forms of Microsoft, which will be filled by the health care personnel of the study team of the Experimental Center and which will be accessible to EMOLED staff of the Clinical Affairs Area. Specifically: in the Form "Patient Card", to be filled in during the enlistment phase, general clinical information is collected (alphanumeric ID associated with the enlisted patient, anamnesis, check of inclusion/exclusion criteria, Braden scale, etc.); in the Form "Patient Card Integration", also to be completed during the enlistment phase, are reported comorbidity, drug therapies and any allergies; while in the last Form "Patient Visit" the data relating to each of the three weekly visits provided for by the protocol are entered, namely those relating to the parameters of the PUSH scale (size of the lesion, exudate and type of tissue), the dressings and any notes.

The Braden scale, present in the Form "Patient Card", is used to assess the risk of the onset of pressure ulcers and, in particular for patients in prolonged stay or who are not able to move in total autonomy, is an assessment to be repeated at least once a week. The Braden scale takes into account 6 factors: sensory perception (ability to respond to discomfort dictated by compression), moisture of the skin (sweating, moisture linked to possible urinary and/ or fecal incontinence), motor activity (level of physical activity), mobility (ability to control/change the position of the body), nutrition (an adequate intake of calories, proteins, vitamins and minerals is essential to prevent the onset of new lesions) and, finally, friction and slipping (the friction force created with the solid surface and/or the linen can accelerate the onset of PU). Variables are ascribed to each factor and it is interpreted according to the principle that the lower the value resulting from the sum of all scores, the higher the risk of injury.

In the mentioned forms, the anonymity of patients will be guaranteed through the association of the patient's sensitive data with a progressive numerical ID. The register of this association will be accessible only to the medical staff of the structure that is part of the study team.

Photographic images acquisition

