For the purposes of this clinical trial, the data referred to in Article 4 No. 1 of the GDPR and data falling into the "particular" categories of personal data, in particular health data referred to in Article 9 of the GDPR, will be processed. The Principal Investigator is identified by the involved investigator site as an authorized person to be treated in accordance with Article 29 of the GDPR, as a person designated in accordance with Article 2 quaterdecies of the Code, and must acquire from the patient duly informed the consent document as well as to participate in the trial, also to the processing of data, after having informed clearly and completely, before the trial begins, each patient about the nature, purpose, results, consequences, risks and methods of processing personal data.

In the event of a personal data breach, the Principal Investigator informs the involved investigator site without undue delay after becoming aware of the breach. The involved investigator site shall notify the competent supervisory authority of the infringement without undue delay and, where possible, within 72 hours of becoming aware of it. Where the notification to the supervisory authority is not made within 72 hours, it shall be accompanied by the reasons for the delay. The notification should describe the nature of the personal data breach including the approximate number of subjects concerned, the contact details of the data protection officer, the likely consequences of the personal data breach and the measures taken or to be taken to fix the personal data breach and also, where appropriate, to mitigate its possible adverse effects. If the breach of personal data presents a high risk to the rights and freedoms of natural persons, the involved investigator site shall communicate in plain and clear language the nature of the breach to the data subject without undue delay, unless the data controller has made personal data incomprehensible to anyone who is not authorized to access it, or has subsequently adopted measures to avoid the occurrence of a high risk for the rights and freedoms of the subjects.

Clinical evaluation plan deviations

In the case of minor and isolated deviations from the protocol, these are recorded in the case report form, which is provided with a space to record any changes or comments the doctor deems appropriate (e.g. treatment not carried out, change of dressing applied, lack of a detection).

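### The visit form as described has no prompted local-reaction item, so a blank note cannot be told from a clear inspection; this adds to the small-sample limit on a zero safety count.

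*Combined protocol and SAP*

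**What the plan says.** **Endpoint.** Study Objectives names safety as an aim. Secondary endpoints measures it by the number of related adverse events in the two groups, and Statistical analysis plans a descriptive summary only.

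**Forms.** Case Report Forms lists the content of the Patient Visit form: the data entered are "namely those relating to the parameters of the PUSH scale (size of the lesion, exudate and type of tissue), the dressings and any notes". The source document is "the form of injury assessment already present at the Investigator Centre", which is not reproduced.

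**Other routes.** Ethical considerations provides a questionnaire on discomfort and says the risk/benefit check will take account of "any adverse events / device-related accidents or non-serious side effects reported by the main investigators". Clinical evaluation plan deviations mentions the case report form, "which is provided with a space to record any changes or comments the doctor deems appropriate". The vigilance sections (Definitions, Reporting by health professionals, Conditions under which a report is not required) count undesirable side effects as accidents, ask staff to report lesser problems to the manufacturer, and describe a reporting form for users.

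**What to look at.** The literature review calls it essential "to consider the condition of the peri-lesional skin (erythema, edema, hardening, maceration"). None of these four signs is a PUSH item. The section on conditions for not reporting names one foreseeable local effect: hyperpigmentation around the wound that fades within tens of seconds.

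**Patients.** Calculation of the sample number says that blue light has not been used clinically in this lesion type, and recruits partly from a severe brain injury unit. Informed consent procedures allows consent by a relative, caregiver or guardian.

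**Temperature.** The principle-of-operation section says that "the treatment induces a temperature between 45 and 50 °C in the treated area". The section on in-human observations reports thermal-camera findings: "due to the compromised condition of the tissues surrounding the ulcers, the baseline temperature of the limb is lower than normal", and "both during and after treatment with the EmoLED device, the temperature never exceeds 40°C".

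**The concern.** The safety endpoint depends on reactions being noticed and written down. The form completed at every visit asks about size, exudate, tissue and dressings, and leaves everything else to free text. A burn that persists would probably be seen, because staff handle the lesion at all 12 visits. A milder or short-lived reaction might not be written down, and some of these patients may not be able to report it themselves. At analysis, an empty notes field could mean that the skin was checked and was normal, or that nobody considered the question.

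This matters because the trial will supply early safety information for blue light on pressure ulcers. If it reports no related events, readers will want to know how far that reflects active looking.

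**Working it through.** **1. The plan's own figures.** The protocol gives no precision target for safety, so there is none to reproduce. The one figure in the thermal background that can be rebuilt is the dose. At 120 mW/cm² (Information about the medical device) for 60 s, 0.120 × 60 = 7.2 J/cm², which agrees with the stated value of about 7. The 30 s exposure given for the mouse observations and the first human study corresponds to 0.120 × 30 = 3.6 J/cm². This checks the dose only; the temperatures cannot be derived from the documents.

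**2. What each route can capture.**

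| Route | Prompted for a local reaction? | Limit |
|---|---|---|
| Patient Visit form | No, notes only | Blank is ambiguous |
| Case report form comments | No | Described for deviations and remarks |
| Investigator reports, vigilance routes | No, spontaneous | Someone must first notice and judge it worth reporting |
| Discomfort questionnaire | Asks about discomfort | Not in the visit schedule, form descriptions or analysis; depends on the patient's ability to answer |
| Photographs | Not applicable | V1, V4, V7, V10 and V12, so 5 of 12 visits, all before irradiation; they can show a lasting reaction but not a same-day one |

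**3. What a zero count allows.** Exact one-sided 95% upper bound with no events: U = 1 − 0.05^(1/n). The planned evaluable treated group is 10 per stage, 20 in all.

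- n = 20: 1 − 0.05^(1/20) = 13.9%.
- n = 10 (one stage): 1 − 0.05^(1/10) = 25.9%.
- n = 15 (if a quarter of the 20 were lost): 18.1%.
- n = 26 or 27 (if 40/0.75 ≈ 53 are enrolled and non-completers are kept): 10.9% or 10.5%.

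These bounds come from n alone and assume that every reaction is recorded.

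**4. What incomplete recording would add.** Let s be the share of patients with a reaction whose reaction is recorded. The documents give no value for s, so these are assumptions. For n = 20 the bound on the true rate becomes U/s, and the chance of recording none at true rate p is (1 − p·s)^20.

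| s | Upper bound, n = 20 | P(none recorded), p = 10% | P(none recorded), p = 5% |
|---|---|---|---|
| 1.00 | 13.9% | 12.2% | 35.8% |
| 0.50 | 27.8% | 35.8% | 60.3% |
| 0.25 | 55.6% | 60.3% | 77.8% |

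At s = 0.75 the bound is 18.5%. A prompted item cannot improve on the first row. It makes the assumption behind that row easier to defend.

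**5. The temperatures side by side.** The stated values differ by 45 − 40 = 5 °C to 50 − 40 = 10 °C. The higher one sits in an argument for the treatment duration, directly after the 60 s figure and followed by a finite element model. The lower one is a thermal-camera observation in patients with chronic lesions, with a comment about the limb. Neither refers to the other, and no reading is given for the sacrum, which the inclusion criteria admit.

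**The case against.** The strongest objection is that the weakness of a zero count comes from having 20 treated patients, which no form can change. The protocol already presents the trial as a proof of concept sized on recruitment capacity. This stands: the missing prompt is an addition to the small-sample limit, not its cause.

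Second, free text is not the only route. Investigator reports, the vigilance duties and the manufacturer's reporting form all exist. This also stands, but they are spontaneous and do not record that someone looked and found nothing.

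Third, the centre's form and the questionnaire are not reproduced, so either might contain a suitable item. The point therefore applies to the forms as described.

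Fourth, redness, swelling and maceration are common around pressure ulcers. An open-ended item would collect noise, and unmasked staff would then judge relatedness. This is fair, and it shapes the wording and tabulation proposed below.

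A reader might infer more from the two temperatures: that the protocol contradicts itself, or that a thermal hazard goes unmonitored. The documents do not support this. The higher figure reads naturally as a design value for the 60 s exposure. The lower one states its method and population, and offers the cool limb as a partial explanation. A design value and an observation can differ without either being wrong. The animal study reported no thermal damage beside the wound. The earlier human experience and routine use since 2018 are described as free of adverse events.

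**Conclusion.** The point holds as a cheap improvement to data capture, with medium confidence. The Patient Visit form as described has no solicited local-reaction item, so the safety endpoint relies on volunteered reports and on a questionnaire that some patients may be unable to answer. A zero count in 20 treated patients would be compatible with a true rate up to 13.9% (25.9% within one stage) under complete recording. Under the assumption that only half are recorded, the figure for 20 would be 27.8%. The first figures reflect sample size; only the gap between them concerns the form, and its actual size is unknown because the documents give no recording rate.

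The conclusion assumes that the unseen centre form and questionnaire hold no equivalent item. It does not say that safety capture is absent, that the device causes burns, or that the treatment parameters should change. The unreconciled temperatures are a matter of background text and would not support a finding by themselves.

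**What to change.** Add one staff-observed yes/no item to the existing Patient Visit form, at every visit and worded identically in both arms: *new or worsened local reaction of the lesion or surrounding skin (e.g. burn, blister, new erythema or edema) since the last visit or still present when the dressing is applied*. A yes is described in the notes field and assessed for relatedness.

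- Record the transient hyperpigmentation separately, as an expected effect.
- Tabulate all yes answers by arm regardless of relatedness, beside the planned count of related events. Controls cannot have a device-related event, so the related count alone gives no like-for-like comparison.
- As an editorial edit only, state the setting of each temperature (model or observation, exposure time, body site) and, if so, that no sacral reading exists.

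**Cost.** 40 × 12 = 480 entries, or about 53.3 × 12 = 640 if enrolment allows for 25% drop-out. No extra visit or procedure is needed, since staff already assess the lesion and care for the surrounding skin. The item will pick up some background change, and unmasked staff may over-record in the treated arm. It may need an amendment, and a substantive one suspends the trial until approved, so it is best made before enrolment or together with another change.
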